## 7. STATISTICAL CONSIDERATIONS

Using intention-to-treat principles, we will compare the primary outcome (Modified COVID Ordinal Outcomes Scale score to Day 15) between patients in each intervention group and the control group using a proportional odds model, adjusted for the following co-variables: age, gender, and duration of acute respiratory infection symptoms prior to randomization. The proportional odds assumption will mainly be examined using graphical methods—e. g., the logit of the empirical cumulative distribution function of the ordinal scale should be parallel among categories of covariates. If proportionality is clearly violated, we will consider partial proportional odds or non-proportional odds models.

With type I error of 0.05, enrolling 540 patients in the primary population will provide 90% power to detect an odds ratio of 1.75. Accounting for a ~10% loss to follow-up rate, we will plan to enroll **600 patients**. This sample size and power assumes a frequentist analysis, which is generally more conservative than what is needed for a Bayesian approach. We will plan an initial DSMB evaluation of safety and feasibility after n=100 patients have been enrolled; efficacy will not be considered at these analyses. The trial will then have frequent interim analyses with details on specifics on timing of meetings, as well as efficacy and futility stopping rules to be detailed in the Statistical Analysis Plan, to be finalized prior to the first interim analyses.

Additional analyses will include comparisons of secondary outcomes between treatment groups. We will compare the Modified COVID Ordinal Outcome Scale daily over the 14-day intervention period using a recently developed longitudinal proportional odds model that can incorporate the information on intermediate states between baseline and Study Day 15. For time-to-event outcomes we will utilize survival models (e.g., Cox proportional hazards models), continuous outcomes will utilize linear regression, and dichotomized outcomes will be evaluated using logistic regression. We will also evaluate primary and main secondary outcomes in key subgroups of interest. *A priori* subgroups for analysis will include age, sex, race/ethnicity, facility residence, BMI, baseline renal function, hypertension, diabetes, cardiovascular disease, and duration of respiratory symptoms.

The proposed trial will use a Bayesian approach to implement adaptive elements and to estimate the primary outcome using the proportional odds model to calculate the posterior probability that the OR > 1, suggesting any benefit. Additionally, we will calculate posterior probabilities to account for the potential that a treatment is ineffective (e.g., OR < 1) or causes harm (i.e., safety concerns) and would be of consideration to terminate enrollment due to futility. A Bayesian approach provides the ability for frequent updating of the posterior probabilities to rapidly identify if a treatment is showing benefit to reducing hospitalization and severity of disease, providing the possibility of more quickly identifying beneficial treatments. The proposed design may evolve as more is learned about COVID-19 and the

treatment responses, with an adaptive Bayesian design that we expect to be more efficient and flexible being in active development.

We expect that given the circumstances of this trial during a rapidly evolving pandemic, the DSMB will need maximum latitude in modifying this trial if necessary, based on other studies of lopinavir/ritonavir that may be conducted simultaneously and the rate of growth or decline of the epidemic. Alterations may include adding patients, adding arms to the trial, declining to stop for futility, or stopping earlier to make the results public if that is necessary. We may also need to collapse categories within the Modified COVID Ordinal Scale based on granularity of data or frequency of an individual category. We are exploring other possible statistical plans that will be included in a final statistical analysis plan and will be presented to the DSMB before the first interim report.

## **8. DATA QUALITY MONITORING AND STORAGE**

### **8.1 Data Quality Monitoring**

We will review data quality remotely using front-end range and logic checks at the time of data entry and back-end monitoring of data using application programming interface tools connecting the online database to statistical software to generate data reports.

### **8.2 Data Storage**

Site personnel will enter study data into a secure online database. Site personnel will maintain the data in the secure online database until the time of study publication. At the time of publication, DCC will generate a de-identified version of the database.

## **9. RISK ASSESSMENT**

### **9.1 Potential Risk to Participants**

Although lopinavir/ritonavir are FDA approved medications with a long history of patient use and well-established safety profiles, potential risks exist to participating in this study of lopinavir/ritonavir versus placebo for the treatment of COVID-19.

#### **9.1.2 Potential risks of receiving lopinavir/ritonavir**

The safety and tolerability of lopinavir/ritonavir has been well characterized through clinical trials and post-marketing experience since first authorization for use in 2001 for the approved HIV indication with over 7 million patient years of exposure. Based on clinical trials and post-marketing experience, the most frequently reported adverse drug reactions among patients receiving lopinavir/ritonavir were gastrointestinal disorders (including diarrhea, nausea, vomiting, and upper and lower abdominal pain), fatigue/asthenia, respiratory tract infection (upper and lower), lipid elevations (hypercholesterolemia and hypertriglyceridemia), musculoskeletal pain (including arthralgia and back pain), and headache (including migraine). Key safety concerns include metabolic abnormalities such as dyslipidemia and insulin resistance, pancreatitis, and hepatotoxicity. In addition, in the HIV population, immune reconstitution inflammatory syndrome (IRIS) manifesting as autoimmune disorders (such as Grave's disease) has been reported.

Important potential risks include PR prolongation at therapeutic dosing, and QT prolongation with supratherapeutic doses. Lopinavir/ritonavir interacts with several drugs since it is an inhibitor of the P450 isoform CYP3A and is likely to increase the plasma concentration of drugs that are metabolized by CYP3A4. Therefore, LPV/r should not be co-administered with drugs primarily metabolized by CYP3A and for which elevated plasma concentrations are associated with serious and/or life-threatening events. A list of such products is included in the lopinavir/ritonavir label. Rare reports of second- or third-degree atrioventricular block in patients with underlying structural heart disease and pre-existing conduction system abnormalities, or in patients receiving drugs known to prolong the PR interval such as verapamil, have been reported in patients receiving lopinavir/ritonavir. Lopinavir/ritonavir should be used with caution in such patients. In addition, QT prolongation with supratherapeutic doses and when lopinavir/ritonavir is co-administered with drugs known to prolong the QT interval has been reported. Because lopinavir/ritonavir is principally metabolized by the liver, caution should be exercised when administering this drug to patients with impaired hepatic function. Extra monitoring is recommended when diarrhea occurs. The relatively high frequency of diarrhea during treatment with lopinavir/ritonavir may compromise the absorption and efficacy (due to decreased compliance) of lopinavir/ritonavir or other concurrent drugs. Serious persistent vomiting and/or diarrhea with lopinavir/ritonavir use might also compromise renal function. The safety of lopinavir/ritonavir for treatment of patients with COVID-19 disease is unknown. COVID-19 may be associated with cardiac effects. lopinavir/ritonavir may prolong QT at supratherapeutic doses and prolong PR at therapeutic doses, resulting in arrhythmias.

### **9.1.3 Potential risks of receiving placebo with COVID-19**

One potential risk to participating in this study is receiving placebo rather than lopinavir/ritonavir. This risk is only relevant if lopinavir/ritonavir are ultimately found to be an effective therapy for COVID-19 and is not relevant if lopinavir/ritonavir are both ultimately found to be ineffective therapy for COVID-19. This trial protocol minimizes this risk through rigorous design to minimize the number of patients that we must enroll to determine whether these therapies are an effective therapy for COVID-19 and allocating approximately one-third of eligible patients to placebo (instead of one half in a traditional two-arm trial). We will also exclude patients who decline to participate because they feel their optimal care requires lopinavir/ritonavir, exclude patients whose treating clinicians declines to allow enrollment because they feel the patient's optimal care requires treatment with lopinavir/ritonavir, and specify procedures for stopping the study drug, unblinding, and allowing open-label administration of lopinavir/ritonavir for patients who experience clinical deterioration during the study period.

## **9.2 Minimization of Risk**

Federal regulations at 45 CFR 46.111(a)(1) require that risks to participants are minimized by using procedures which are consistent with sound research design. This trial protocol incorporates numerous design elements to minimize risk to patients that meet this human subject protection requirement. Lopinavir/ritonavir is approved by the U.S. Food and Drug Administration and have been used in clinical practice for decades in a number of patient populations with an established safety profile. The dose and route of administration of both medications in this trial are comparable to the dose and route of administration approved for the treatment of other acute infections, such as HIV-1. The duration of treatment in this trial of 14 days is significantly shorter than for treatment of HIV-1 infection, for which the drug is frequently administered for multiple years. To further mitigate risk, we will exclude patients

with specific risk factors for adverse events from study medication, we will exclude patients with higher risk for adverse events and patients receiving medications that may interact with lopinavir/ritonavir.

We will collect data on adverse events that are significant enough to warrant health care evaluation. It was determined that transient, and clinically insignificant changes in the electrocardiogram or laboratory testing would not be required. In addition, the additional risk to the public and to research personnel by exposing them to COVID-19 patients by requiring additional research testing is greater than the benefits of this monitoring. The trial protocol includes active monitoring of clinically significant adverse events, clinical outcomes, and interim analyses by an independent data and safety monitoring board empowered to stop or modify the trial at any time, including the need to request additional safety monitoring if determined to be warranted.

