22. Currently prescribed (with planned continuation) or planned administration during 14-day study period of any of the following medications: alfuzosin, apalutamide, astemizole, ergot-containing medicines (including dihydroergotamine mesylate, ergotamine tartrate, methylergonovine), lomitapide, lovastatin, lurasidone, midazolam, phenobarbital, phenytoin, ranolazine, rifampin, sildenafil, simvastatin, rivaroxaban, St. John's Wort, terfenadine, triazolam. Patients who are on warfarin or fluticasone will be advised to contact their primary care provider to advise them that they are in the trial and possibly receiving lopinavir/ritonavir which can influence levels of either drug and may require more frequent monitoring.

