### 3.3 Justification of Exclusion Criteria

Since this is intended as an outpatient trial, patients hospitalized within 6 days prior to enrollment/randomization are excluded. The other exclusion criteria are primarily designed for patient safety. In addition to excluding specific vulnerable populations (e.g., prisoners), these criteria are designed to exclude patients for whom receipt of lopinavir/ritonavir might increase the risk of serious adverse events. Lopinavir/Ritonavir has been routinely prescribed to outpatients with HIV-1 without extensive cardiac workups, laboratory testing, or monitoring. In addition, we have incorporated guidelines for safe outpatient prescribing of lopinavir/ritonavir without a baseline electrocardiogram or outpatient cardiac monitoring and have put into place a method of monitoring newly prescribed medications during the 14-day intervention period.

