### **3.5 Assessment of Eligibility and Exclusion Tracking**

For patients who appear to meet eligibility criteria after screening, we will complete an electronic case report form to determine eligibility and track exclusions. We will access and store the electronic case report form in the electronic database. At the time of entry into the screening database, we will assign the patient a screening number.

If a patient appears to meet all eligibility criteria, the site investigator or delegate will approach the patient to confirm eligibility, discuss potential study recruitment, and proceed with informed consent. Most patients will no longer be in the healthcare setting and therefore we anticipate that this discussion will occur primarily by telephone or videophone to the patient's home (test pending patients are typically advised by their clinicians to home quarantine while symptomatic and test results are pending). We may advertise the study at both the testing sites as well as more broadly.

For all excluded patients, including refusal by the patient to participate, we will collect a small number of variables, including month and year patient met screening criteria and reason(s) patient was excluded to allow for reporting in the CONSORT diagram of the manuscript. Due to the nature of this trial in the outpatient setting and for staff safety and personal protective equipment (PPE) conservation, these encounters will usually occur via telephone or videophone.

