## **4. STUDY INTERVENTIONS**

### **4.1 Treatment of Study Participants**

A summary of the trial’s schedule of events is included in Appendix A.

Timing of study procedures is based on the time of randomization, which is defined as “Time 0”. Study Day 1 is defined as the day of receipt of the first dose of study drug. We will assess the primary outcome on Study Day 15, which corresponds to 14 days (2 weeks) after the initiation of study drug.

A research physician will prescribe a study medication that a central pharmacy (Belmar Pharmacy) will fill at no charge to the patient and will arrive through overnight mail (typically next day by 10:00AM). The study medication will arrive in blinded blister packs labelled as lopinavir/ritonavir or placebo with the appropriate daily instruction for administration. The goal is initiation of treatment within one day of randomization (Study Day 1).

On Study Days 1-15, the patient will complete brief electronic data collection form through a secure electronic platform that will confirm receipt and administration of study drug and document the number and reason for any missed doses. For those with missing electronic data, telephone follow-up will provide an additional opportunity to clarify study drug administration, as needed. If the participant is hospitalized prior to completion of the study medication, an attempt will be made to continue study medication. However, study medication may be discontinued if felt necessary by the treating clinician in consultation with the local investigator. Unblinding will occur only if required for subject safety or treatment at the request of the treating clinician.

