### **4.5 On-Study Monitoring**

All participants enrolled in the study will be outpatients (not hospitalized) and therefore initial monitoring will be remote as part of routine outpatient clinical care with treating physicians and nurses (we anticipate primarily virtual care/telehealth or routine telephone follow-up). The research staff will provide additional remote monitoring through daily electronic collection of symptoms, healthcare utilization, clinically obtained electrocardiograms, newly prescribed medications, and adverse event reporting with supplemental telephone follow-up as needed. The research team may flag potential issues but will defer specific decisions about additional care and hospital transfer to usual outpatient clinical care.

Lopinavir/ritonavir has been used extensively for outpatient treatment of other conditions without the need for additional monitoring during short term therapy.

Between baseline and Study Day 15, study personnel will ascertain and review the initiation of any new medications daily and evaluate for potential medication interactions with lopinavir/ritonavir (see Appendix B). If a medication that is considered to be contraindicated with lopinavir/ritonavir is discovered, site physician investigator or designee will contact the patient to discuss if stopping study drug is appropriate or if the medication in question may be stopped or substituted in consultation with the prescribing/treating clinician. If a medication with a potential interaction with lopinavir/ritonavir is identified, study personnel will contact the treating clinician to ensure they are aware of the potential interaction, as needed. Treating clinicians will determine whether an alternative medication would be

appropriate or whether the risk-benefit ratio favors continuing the medication with the known potential interaction.

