## 13. APPENDICES

### Appendix A. Schedule of Events

#### Schedule of Events

Description:	Date of Randomization	Days 1-14	Days 15-16	Day 29
Confirmation of SAR-CoV-2 positive test result	X			
Home medications	X			
Verification of Inclusion/Exclusion Criteria	X			
Remote consent	X			
Randomization	X			
IP shipped to subject	X			
Self-Administered Dosing		X		
Self-Reported Symptom Survey		X	X	X
Assessment of Adverse Events		X	X	X
Modified COVID Ordinal Outcome Scale		X	X	X
Ventilator Status		X	X	X
ICU Status		X	X	X
Oxygen Status		X	X	X
Hospital Length of Stay		X	X	X
Vital Status				X
End of Study				X

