## **Appendix B. Potential medication interactions with lopinavir/ritonavir**

Medications considered to present a potential interaction with lopinavir/ritonavir, which if ordered during the 14-day study period, will prompt study personnel to discuss with treating clinicians the risk-benefit assessment of this medication and potential need for additional monitoring: flecainide, mefloquine, methotrexate, mexilitine, rifampicin, rifapentine, amiodarone, cimetidine, dofetilide, phenobarbital, phenytoin, or sotalol, propafenone, astemizole, terfenadine, alfuzosin, apalutamide, ranolazine, dronedarone, rifampin, lurasidone, cisapride, pimozide, ergot-containing medicines (including dihydroergotamine mesylate, ergotamine tartrate, methylergonovine), lovastatin, simvastatin, lomitapide, sildenafil, triazolam, midazolam, rivaroxaban, fluticasone and anticoagulants or St. John's Wort.

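### Current users of several Appendix B drugs are neither excluded nor reviewed, because the interaction check is written only for newly started drugs

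*Protocol*

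**What the plan says.** Protocol Section 9.2 lists exclusion as one of the ways risk is reduced. It states without qualification that the trial will exclude "patients with higher risk for adverse events and patients receiving medications that may interact with lopinavir/ritonavir".

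Section 3.2 gives the working criteria. Item 21 names drugs with a high risk of QT prolongation and item 22 names further drugs; current users with planned continuation are excluded under both. Item 22 then treats two drugs differently: "Patients who are on warfarin or fluticasone will be advised to contact their primary care provider".

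After enrollment, three places describe the interaction check:

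- Section 3.3 says the investigators "have put into place a method of monitoring newly prescribed medications during the 14-day intervention period".
- Section 4.5 says that "study personnel will ascertain and review the initiation of any new medications daily and evaluate for potential medication interactions with lopinavir/ritonavir".
- Appendix B lists the potentially interacting drugs, "which if ordered during the 14-day study period, will prompt study personnel to discuss with treating clinicians the risk-benefit assessment".

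Three steps before dosing could also bear on the point. The schedule of events in Appendix A has a row for "Home medications" on the date of randomization. Section 3.5 says "the site investigator or delegate will approach the patient to confirm eligibility". Section 4.1 says "A research physician will prescribe a study medication that a central pharmacy" will fill.

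**The concern.** Two parts of the protocol do not meet. Section 9.2 tells an ethics board that patients on interacting drugs are kept out, yet some drugs on the protocol's own interaction list are absent from the exclusions. The check that might act as a backstop begins only when a new drug is started or ordered.

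A patient already taking one of the uncovered drugs therefore passes between the two. This is the wrong way round for exposure: a drug started on Day 3 overlaps with study drug for part of the 14 days, while an ongoing drug can overlap with all 28 doses.

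The later safeguards depend on routine care. Section 4.6 stops the study drug for a QTc of 500 ms or more, but only if an EKG was obtained clinically. Section 6.2 collects laboratory results only if tests were done. The trial is remote and mandates no study ECG or laboratory test, so medication review before shipment is one of its few preventive measures.

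**Working it through.** The documents state no count of these drugs, so there is no plan figure to reproduce. The check is a comparison of lists by name, followed by a reading of the text that governs current users.

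**Inputs**

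- Appendix B: 34 entries, counting the ergot-containing medicines as one.
- Exclusion 21 (Section 3.2): 42 drugs.
- Exclusion 22 (Section 3.2): 18 entries, with the ergot group again counted as one.

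**Step 1: match Appendix B to the exclusions**

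| Source | Appendix B entries matched | Count |
|---|---|---|
| Exclusion 21 | flecainide, amiodarone, cimetidine, dofetilide, sotalol, propafenone, dronedarone, cisapride, pimozide | 9 |
| Exclusion 22 | all 18 of its entries | 18 |
| Either | | 9 + 18 = 27 |

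Unmatched by literal name: 34 − 27 = 7. These are mefloquine, methotrexate, mexiletine (spelled mexilitine in Appendix B), rifampicin, rifapentine, fluticasone and anticoagulants.

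Reading rifampicin as rifampin, which exclusion 22 names, gives 27 + 1 = 28 covered and 34 − 28 = 6 left. Merging the two names into one entry gives 6 of 33.

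**Step 2: what is written for current users of the six**

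| Entry | Rule for a current user |
|---|---|
| Fluticasone | Admitted, advised to contact primary care provider |
| Anticoagulants: rivaroxaban | Excluded |
| Anticoagulants: warfarin | Admitted, advised to contact primary care provider |
| Anticoagulants: all others | None |
| Mefloquine | None |
| Methotrexate | None |
| Mexiletine | None |
| Rifapentine | None |

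That leaves four named drugs and part of one class with no entry rule.

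**Step 3: does the interaction check reach them?**

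| Place | What sets it off |
|---|---|
| Section 3.3 | A newly prescribed drug |
| Section 4.5 | A new drug being started |
| Section 6, telephone follow-up | A newly prescribed drug |
| Appendix B | A drug ordered within the 14 days |

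None of these is set off by uninterrupted use of a drug begun before enrollment. A refill ordered within the window might be.

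**Step 4: do the steps before dosing reach them?** Home medications are recorded, eligibility is confirmed and a physician prescribes the study drug, but no passage tells anyone to compare the home-medication list with Appendix B. Eligibility review tests the listed criteria, and Step 2 shows that these drugs are not among them.

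**The case against.** The strongest counter-argument is that the text is ambiguous, not silent. Section 4.6 stops study drug when daily monitoring shows an interaction with a drug the patient needs and the clinicians and investigator judge the combination unsafe; it does not say the drug must be new. Section 4.5 speaks of contacting the clinician once an interacting medication is identified, again without the word new. Section 11 mentions newly prescribed medications only as an example of what is monitored. These points soften the case but do not close the gap. The daily monitoring in Section 4.6 is the review that Section 4.5 describes, and that review starts from new drugs. The Section 4.5 action sentence follows directly from the same review. The example in Section 11 creates no check of its own.

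A second argument is that the tiers are deliberate: some drugs exclude, others call for discussion. The provision for warfarin and fluticasone shows that the authors thought about ongoing users. This may well be so, and it is a fair reason not to demand that all six entries become exclusions. It does not explain why the discussion tier applies to new orders and not to ongoing use.

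Third, Section 9.2 is a narrative summary and Section 3.2 is the operative text. That is true, but Section 9.2 is offered in support of a regulatory requirement to minimize risk, so it should not claim more than Section 3.2 delivers.

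Finally, the documents do not rank the severity of these interactions. Section 9.1.2 reserves its warning against co-administration for drugs primarily metabolized by CYP3A whose raised levels are dangerous, and refers to the label for the list. Nothing in the documents places the uncovered drugs in that group. This objection stands, and it limits how serious the point can be made.

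**Conclusion.** The concern holds. Six of the 34 Appendix B entries do not fully exclude current users. Four named drugs, and anticoagulants other than rivaroxaban and warfarin, prompt no written action when their use is ongoing. A new order for any of them does prompt contact with the treating clinician.

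The count assumes that rifampicin and rifampin are the same drug; matched strictly by name it would be 7 of 34. The conclusion about scope assumes that the monitoring in Section 4.6 is the review described in Section 4.5, which is the natural reading.

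This is a participant-safety rule with too narrow a scope, together with a statement in Section 9.2 that describes a broader exclusion than the trial applies. It should be corrected. The clinical consequence cannot be sized from the documents.

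**What to change.** In Sections 3.5 and 4.5, require the Appendix B check on the home-medication list at eligibility review, before the study drug is shipped. Use the staff-to-clinician contact already written for new orders, and include warfarin and fluticasone users, so that contact does not depend on the patient alone. This leaves no Appendix B entry without a written action for current users.

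Reword Section 9.2 to say that some interacting drugs exclude a patient and others lead to review. Which drugs belong in which tier is for the sponsor to decide.

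The cost is protocol wording and one screening step on data already collected. It will mean some calls before shipment and possibly a few exclusions or short delays. The delays matter because Section 4.1 aims to start treatment within one day of randomization, so the check is best done before randomization, while eligibility is being confirmed.
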